7.2.1.1. Time period and Frequency for collecting AE and SAE information

- Any SAEs assessed as related to study participation (e.g., protocol-mandated procedures, invasive tests, or change in existing therapy) or related to a GSK product will be recorded from the time a subject consents to participate in the study up to and including any follow-up contact.
- AEs will be collected from the start of Study Treatment until the follow-up contact (see Section 7.2.1.3), at the timepoints specified in the Time and Events Table (Section 7.1).
- Medical occurrences that begin prior to the start of study treatment but after obtaining informed consent may be recorded on the Medical History/Current Medical Conditions section of the CRF.
- All SAEs will be recorded and reported to GSK within 24 hours, as indicated in [Appendix 4](#).

- Investigators are not obligated to actively seek AEs or SAEs in former study subjects. However, if the investigator learns of any SAE, including a death, at any time after a subject has been discharged from the study, and he/she considers the event reasonably related to the study treatment or study participation, the investigator must promptly notify GSK.

NOTE: The method of recording, evaluating and assessing causality of AEs and SAEs plus procedures for completing and transmitting SAE reports to GSK are provided in [Appendix 4](#)

7.2.1.2. Method of Detecting AEs and SAEs

Care will be taken not to introduce bias when detecting AEs and/or SAEs. Open-ended and non-leading verbal questioning of the subject is the preferred method to inquire about AE occurrence. Appropriate questions include:

- “How are you feeling?”
- “Have you had any (other) medical problems since your last visit/contact?”
- “Have you taken any new medicines, other than those provided in this study, since your last visit/contact?”

7.2.1.3. Follow-up of AEs and SAEs

After the initial AE/SAE report, the investigator is required to proactively follow each subject at subsequent visits/contacts. All SAEs, and non-serious AEs of special interest (as defined in Section [4.6.1](#)) will be followed until resolution, until the condition stabilizes, until the event is otherwise explained, or until the subject is lost to follow-up (as defined in Section [5.4](#)). Further information on follow-up procedures is given in [Appendix 4](#).

7.2.1.4. Regulatory Reporting Requirements for SAEs

Prompt notification by the investigator to GSK of SAEs related to study treatment (even for non- interventional post-marketing studies) is essential so that legal obligations and ethical responsibilities towards the safety of subjects and the safety of a product under clinical investigation are met.

GSK has a legal responsibility to notify both the local regulatory authority and other regulatory agencies about the safety of a product under clinical investigation. GSK will comply with country specific regulatory requirements relating to safety reporting to the regulatory authority, Institutional Review Board (IRB)/Independent Ethics Committee (IEC) and investigators.

Investigator safety reports are prepared for suspected unexpected serious adverse reactions according to local regulatory requirements and GSK policy and are forwarded to investigators as necessary.

An investigator who receives an investigator safety report describing a SAE(s) or other specific safety information (e.g., summary or listing of SAEs) from GSK will file it with the IB and will notify the IRB/IEC, if appropriate according to local requirements.

7.2.2. Physical Exams

- A complete physical examination will include, at a minimum, assessment of the Cardiovascular, Respiratory, Gastrointestinal and Neurological systems. Height and weight will also be measured and recorded. This will be carried out at screening and follow up.
- A brief physical examination will include, at a minimum assessments of the skin, lungs, cardiovascular system, and abdomen (liver and spleen). To be carried out at the start of each period.
- Investigators should pay special attention to clinical signs related to previous serious illnesses.

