- *Height and weight removed at follow-up (not required).*
- *Spirometry added at screening (see justification in Section 5.1).*
- *Immunogenicity moved from screening to Day 1, Treatment Period 1.*
- *Removal of exploratory ventilatory parameters after exercise, as this assessment would delay the echocardiogram, which is the primary endpoint.*
- *Addition of telemetry throughout the treatment periods.*
- *Correction of typographical errors.*

Section 7.1.1: Screening and Follow up

Procedure	Screening ¹ (up to 28 days prior to Treatment Period 1, Day 1)	Follow up (7-10 days post last dose)	Notes
Informed consent	X		
Inclusion and exclusion criteria	X		
Demography	X		
Full physical exam, including height and weight	X	X	Height and weight to be measured at screening only. Weight at screening will be used for dosing calculation.
Alcohol, Drugs of Abuse, Smoking test	X		
Medical history (includes substance usage [and family history of premature CV disease])	X		Substances: Drugs, Alcohol, tobacco
Past and current medical conditions [including cardiovascular medical history]	X		
Serum OR urine pregnancy test (WCBP)	X		
HIV, Hep B and Hep C screen	X		
Laboratory assessments (include liver chemistries)	X	X	Non Fasting
Immunogenicity	X	X	
12-lead ECG	X	X	TriPLICATE ECG required at screening.
Vital signs	X	X	TriPLICATE vital signs required at screening.
Spirometry	X		
Echocardiogram	X		
Concomitant Medication review	X	X	
Hypoxia chamber plus exercise	X		Tolerance to 4000m for 10 mins followed by followed by incremental exercise testing to determine maximum oxygen uptake (VO2max) and calculate 70% of VO2max for the (to be used for the exercise challenge during the Treatment Periods).
Pharmacogenetic sample (PGx)	X		Can be taken any time after consent has been signed. Only required once and is optional.
AE/SAE review	X	X	As per timings detailed in Section 7.2.1.1

1. Screening assessments are allowed to be conducted on more than one day

Section 7.1.2: Treatment Period 1 and 2

Procedure	Treatment Period 1 and 2 (Washout 3-14 days)										Notes	
	Times relative to start of dosing				Hypoxic Challenge ~80 min (Times relative to entry to Chamber)							
	Pre-dose	0h	15 min	15-45 min	0-60 min	60 min	60-70 min	Immediately after exercise	30min rest On exit from chamber	After 30 min rest		
Randomisation	X										Randomisation can occur up to the day before the first treatment period	
Brief physical exam	X											
Vital signs	X		X					X ⁵		X		

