Rationale for change: Height and Weight removed from follow-up visit, as not required.

- A complete physical examination will include, at a minimum, assessment of the Cardiovascular, Respiratory, Gastrointestinal and Neurological systems. Height and weight will also be measured and recorded, at screening only. ~~This will be carried out at screening and follow up.~~

Section 7.2.3: Vital Signs

Rationale for change: Correction of typographical errors.

- Triplicate measurements will be taken at screening, and single measurements at other time-points. ~~Three readings of blood pressure and pulse rate will be taken. The first reading should be rejected. Second and third readings should be averaged to give the measurement to be recorded in the CRF. (Triplicate measurements will only be taken at screening and single measurements to be taken after that).~~

Section 7.2.4: Electrocardiogram (ECG)

Rationale for change: QTc Stopping Criteria removed from Section 7.2.5, and inserted into Section 5.4 with the other subject stopping criteria.

- Triplicate 12-lead ECGs will be obtained at screening. At all other time-points, a single 12-lead ECGs will be obtained ~~at each time point during the study~~ using an ECG machine that automatically calculates the heart rate and measures PR, QRS, QT, and QTc intervals. Refer to Section 5.4.2 for QTc withdrawal criteria and additional QTc readings that may be necessary.
- ECG to be measured in a semi-supine position after 5 minutes rest.
- The same QT correction formula *must* be used for each individual subject for all QTc data being collected for data analysis. Safety ECGs and other non-protocol specified ECGs are an exception.

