4.2. Treatment Arms and Duration

Figure 2 Subject participation flow

The subjects must participate in the procedures detailed in the Time and Events Table (Section 7.1) and the timings of the simulated altitude, exercise and echocardiograms is shown in [Figure 3](#).

Figure 3 Approximate timing of simulated altitude and echocardiogram measurements (black arrows) during Treatment Periods 1 and 2

There will be a washout period of 3-14 days between treatments to ensure biomarkers return to pre-challenge baseline. Subjects then return to the site and repeat the same procedures as above, except that they will receive the treatment (GSK2586881 or Saline) that they did not receive in the first period.

Follow Up

This will occur up to 10 days after the end of the second treatment period. During the visit various safety tests will be conducted (see time and events table in Section 7.1).

The total study duration for each subject is expected to be a maximum of 56 days.

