4.6.1. Risk Assessment

Potential Risk of Clinical Significance	Summary of Data/Rationale for Risk	Mitigation Strategy
Investigational Product (IP) [GSK2586881]		
Cardiovascular risk	During preclinical testing a brief period of non-sustained ventricular tachycardia was observed in one monkey receiving a dose of 20.8 mg/kg/day.	The dose used in this study is much lower and well below the No observed adverse effect level (NOAEL) for the 14 day repeat dose cynomolgus monkeys of 8 mg/kg/day.
Potential Reproductive/embryofetal risks	Preclinical studies have not been performed	Women of childbearing potential will be excluded from the study.
Potential for Immunogenicity	There has been no induction of an immune response to rhACE2 in either of the clinical studies to date in healthy subjects or participants with ARDS.	Patients will have routine monitoring of any immunological response that may occur. If an immunological response is seen the patient will be asked to return for further monitoring and assessment(s).
Potential for rash	In study ACE114622, rash was reported more frequently in subjects receiving GSK2586881, although only one event was considered drug-related.	Patients will be monitored for rash in the clinical trials.

Potential Risk of Clinical Significance	Summary of Data/Rationale for Risk	Mitigation Strategy
Study Procedures		
Effects of hypoxia (light headiness, headaches, nausea)	The subjects will be exposed to hypoxic conditions for approximately 90 minutes with a simulated altitude of 4000m	The subjects will be continuously observed and monitored with telemetry and pulse oximetry. Stopping criteria are included in the protocol.

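### Rash is a listed drug risk, but no required skin examination follows the drug in placebo-first subjects

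*Protocol*

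**What the plan says.** Section 4.6.1 (Risk Assessment) puts potential for rash under the investigational-product risks. The basis is one earlier study in which "rash was reported more frequently in subjects receiving GSK2586881, although only one event was considered drug-related". The mitigation reads "Patients will be monitored for rash in the clinical trials" and names no examination and no time point.

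Section 7.2.2 (Physical Exams) defines two examinations:

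- The complete one is done at screening and follow-up: "A complete physical examination will include, at a minimum, assessment of the Cardiovascular, Respiratory, Gastrointestinal and Neurological systems".
- The brief one reads "A brief physical examination will include, at a minimum assessments of the skin, lungs, cardiovascular system, and abdomen (liver and spleen"), with the timing "To be carried out at the start of each period". The Time and Events table in Section 7.1.2 marks it in the pre-dose column only.

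The Section 7.2.2 text shown is that of Amendment 01. The Amendment 02 change log (Section 12.6.2.2) revises the complete-examination bullet to limit height and weight to screening, but still asks for "assessment of the Cardiovascular, Respiratory, Gastrointestinal and Neurological systems". Its schedule keeps the full examination in the column headed "Follow up (7-10 days post last dose") and the brief examination before dosing.

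On the interval between doses, Section 4.2 says "There will be a washout period of 3-14 days between treatments".

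**The concern.** The protocol treats skin as worth examining, since it comes first in the brief examination. That requirement falls before each dose. It is missing from the one scheduled examination that follows the drug in every subject. Whether a subject has a required skin check after the drug therefore depends on the randomised sequence.

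What is at stake is how completely a named risk is found. Where no examination item covers skin, a rash is recorded only if the subject mentions it or staff happen to see it. Section 7.2.1.2 prefers open-ended questions, and its examples do not ask about skin. Amendment 02 also removed the reference to following adverse events of special interest, on the ground that none had been defined, so rash has no special follow-up by that route.

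**Working it through.** The plan gives no figure to reproduce. The check traces each required examination against the dosing days.

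**Inputs**

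- Skin required: brief examination yes, complete examination no (Section 7.2.2).
- Brief examination: pre-dose in Periods 1 and 2. Complete examination: screening and follow-up (Sections 7.1 and 7.2.2).
- Washout: 3-14 days (Section 4.2). Follow-up: 7-10 days after the last dose (Section 7.1.1).
- Subjects: about 25 randomised and 20 completing under Amendment 02 (Section 12.6.2); about 35 and 30 in the Amendment 01 text (Section 4.3).
- Allocation: 1:1, as used in the precision simulation of Section 9.2.1.

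**Required skin examinations by sequence, as written**

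| Visit | Skin required? | Drug-first | Placebo-first |
|---|---|---|---|
| Screening (complete) | No | before drug | before drug |
| Period 1 pre-dose (brief) | Yes | before drug | before drug |
| Period 2 pre-dose (brief) | Yes | **3-14 days after drug** | before drug (3-14 days after placebo) |
| Follow-up (complete) | No | after drug | after drug |
| **Required after drug** | | **1** | **0** |
| **Required after placebo** | | **0** | **1** |

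**Drug exposures with no required skin examination afterwards**

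- Amendment 02: 25/2 = 12.5, so 12-13 of 25 randomised; 20/2 = 10 of 20 completers.
- Amendment 01: 35/2 = 17.5, so 17-18 of 35 randomised; 30/2 = 15 of 30 evaluable.

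Either way it is about half. The count for placebo exposures is the same, because the drug-first half has no required skin examination after its Period 2 placebo.

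**With skin added to the complete examination**

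- Placebo-first: 0 + 1 = 1 after the drug, at 7-10 days.
- Drug-first: 1 + 1 = 2 after the drug, at 3-14 days and at (3 + 7) to (14 + 10) = 10-24 days.

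The documents give no rate, onset or duration for rash, so the number of rashes that would be missed cannot be estimated.

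**The case against.** The strongest reply is that no commitment is broken. Section 4.6.1 promises monitoring, not a scheduled skin examination, and collecting adverse events is an ordinary way to monitor for rash. Under Section 7.2.1.1 that collection runs from the start of treatment to the follow-up contact in both sequences. The follow-up examination is a full one with a minimum list, so an examiner is free to look at the skin. Staff are in close contact after every dose, with four echocardiograms, two ECGs, repeated vital signs and repeated blood draws. Section 7.2 also allows physical examinations to be added if new data call for them. A visible rash still present at 7-10 days would probably be recorded anyway, and only one earlier event was considered drug-related.

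Most of this stands, and it limits how much the change can gain. A rash that clears within 7 days would still depend on reporting even with the change. But none of these provisions is a required look at the skin after the drug in placebo-first subjects. The freedom to do more than a minimum does not make the examination uniform across subjects.

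It is also fair to say that the section text shown is from Amendment 01 while the 25 and 20 come from Amendment 02, whose main body is not shown. The Amendment 02 change log repeats the same four systems and the same examination timing, and the affected share is about half under either sample size.

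**Conclusion.** The point holds and is minor. As written, placebo-first subjects have 0 required skin examinations after GSK2586881 and drug-first subjects have 1, so about half of the drug exposures (12-13 of 25 randomised, 10 of 20 completers) have none. This is reduced ascertainment of a listed risk, not a failure to monitor.

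The gap is equal after placebo, so it does not by itself bias the comparison of drug with placebo. The PASP analysis, the success rule and the interim decisions are unaffected.

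The conclusion assumes allocation close to 1:1 and that the current Section 7.2.2 reads as the Amendment 02 change log shows it. The effect on the number of rashes detected is unknown.

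**What to change.** In Section 7.2.2, add skin to the systems that the complete physical examination must cover at a minimum. The follow-up visit 7-10 days after the last dose then includes a required skin check in both sequences: one after the drug for placebo-first subjects and two for drug-first subjects.

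The cost is one word in the protocol. The examination already takes place at that visit with the same staff, so no visit or procedure is added.

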7.2.3. Vital Signs

- Vital signs will be measured in semi-supine position after 5 minutes rest and will include temperature, systolic and diastolic blood pressure and pulse rate. Three readings of blood pressure and pulse rate will be taken.
- First reading should be rejected.
- Second and third readings should be averaged to give the measurement to be recorded in the CRF. (Triplicate measurements will only be taken at screening and single measurements to be taken after that).

7.2.4. Electrocardiogram (ECG)

- Triplicate 12-lead ECGs will be obtained at screening. At all other time-points a single 12-lead ECGs will be obtained at each time point during the study using an ECG machine that automatically calculates the heart rate and measures PR, QRS, QT, and QTc intervals. Refer to Section 7.2.5 for QTc withdrawal criteria and additional QTc readings that may be necessary.
- ECG to be measured in a semi-supine position after 5 minutes rest.

7.2.5. QTc Stopping Criteria

- The *same* QT correction formula *must* be used for *each individual subject* to determine eligibility for and discontinuation from the study. This formula may not be changed or substituted once the subject has been enrolled.
- For example, if a subject is eligible for the protocol based on QTcB, then QTcB must be used for discontinuation of this individual subject as well.
- Once the QT correction formula has been chosen for a subject's eligibility, the *same formula* must continue to be used for that subject *for all QTc data being collected for data analysis*. Safety ECGs and other non-protocol specified ECGs are an exception.

- The QTc should be based on single or averaged QTc values of triplicate electrocardiograms obtained over a brief (e.g., 5-10 minute) recording period

A subject that meets either bulleted criterion below will be withdrawn from the study.

- QTcB or QTcF > 500 msec,
- Change from baseline: QTc >60 msec

7.2.6. Clinical Safety Laboratory Assessments

All protocol required laboratory assessments, as defined in [Table 2](#), must be conducted in accordance with the Protocol Time and Events Schedule. Laboratory requisition forms must be completed and samples must be clearly labelled with the subject number, protocol number, site/centre number, and visit date. Details for the preparation and shipment of samples will be provided by the laboratory and are detailed in the laboratory manual. Reference ranges for all safety parameters will be provided to the site by the laboratory responsible for the assessments.

If additional non-protocol specified laboratory assessments are performed at the institution's local laboratory and result in a change in subject management or are considered clinically significant by the investigator (e.g., SAE or AE or dose modification) the results must be recorded in the CRF.

Refer to the SRM for appropriate processing and handling of samples to avoid duplicate and/or additional blood draws.

Haematology, clinical chemistry, urinalysis and additional parameters to be tested are listed in [Table 2](#).

Table 2 Protocol Required Safety Laboratory Assessments

Laboratory Assessments	Parameters			
Haematology	Platelet Count	RBC Indices:	WBC count with Differential:	
	RBC Count	MCV	Neutrophils	
	Hemoglobin	MCH	Lymphocytes	
	Hematocrit		Monocytes	
			Eosinophils	
			Basophils	
Clinical Chemistry ¹	BUN	Potassium	AST (SGOT)	Total and direct bilirubin
	Creatinine	Sodium	ALT (SGPT)	Total Protein
	Glucose	Calcium	Alkaline phosphatase	Albumin
Routine Urinalysis	
 Specific gravity pH, glucose, protein, blood and ketones by dipstick Microscopic examination (if blood or protein is abnormal) 			
Other Screening Tests	
 HIV Hepatitis B (HBsAg) Hepatitis C (Hep C antibody) Alcohol, smoking and drug screen (to include at minimum: amphetamines, barbiturates, cocaine, opiates, cannabinoids, benzodiazepines and cotinine) performed at site Urine hCG Pregnancy test (as needed) ² 			
NOTES :	
 Details of Liver Chemistry Stopping Criteria and Required Actions and Follow-Up Assessments after liver stopping or monitoring event are given in Section 5.4.2 and Appendix 2. Local urine testing will be standard for the protocol unless serum testing is required by local regulation or ethics committee. 			

All laboratory tests with values that are considered clinically significantly abnormal during participation in the study or within 3 days after the last dose of study treatment should be repeated until the values return to normal or baseline. If such values do not return to normal within a period judged reasonable by the investigator, the etiology should be identified and the sponsor notified.

7.3. Hypoxia Challenge

Each subject will be inside the hypoxia chamber for approximately 80 minutes per period, during which time they will be under the full $4000\text{m} \pm 10\%$. hypoxic conditions

If three or more subjects do not tolerate the hypoxic challenge, either due to symptoms or O2 saturation of <65%, then the simulated altitude will be adjusted in decrements of 500m (i.e. from 4000m to 3500m) for all remaining subjects to a minimum of 3000m.

Further details about the hypoxia challenge is detailed in the SRM.

7.3.1. Exercise Challenge

Subjects will perform an exercise challenge at 70% of maximum VO₂ uptake on a cycle ergometer within the hypoxia chamber for 10 minutes as detailed in the SRM.

Subjects must complete a minimum of 5 minutes exercises at 70% of maximum_{max} VO₂ uptake.

Further details about the exercise challenge is detailed in the SRM.

7.4. Echocardiogram

Echocardiograms will be taken as detailed in the Time and Events table (Section 7.1).

Echocardiograms will be obtained with the subject resting supine or lying on their left side.

PASP will be measured and recorded.

PASP will be determined by measuring maximal tricuspid regurgitation velocity and applying the modified Bernoulli equation to convert this value into pressure values. Estimated right atrial pressure (RAP) must be added to this obtained value.

Further details about the PASP measurement is detailed in the SRM.

Additional echocardiograms may be obtained for each subject as needed (in the judgement of the Investigator and GSK Medical Monitor if required).

Further details can be found in the SRM.

